4.0 Study Design

4.1 Describe and explain the study design (e.g. case-control, cross-sectional, ethnographic, experimental, interventional, longitudinal, observational).

Response: Randomized, split-mouth, double blinded design clinical trial.

5.0 Local Number of Subjects

5.1 Indicate the total number of subjects that will be enrolled or records that will be reviewed locally.

Response:

52 subjects

5.2 If applicable, indicate how many subjects you expect to screen to reach your target sample (i.e. your screen failure rate).

Response:

100 subjects

5.3 Justify the feasibility of recruiting the proposed number of eligible subjects within the anticipated recruitment period. For example, how many potential subjects do you have access to? What percentage of those potential subjects do you need to recruit?

Response:

The school of dental medicine at SUNY at Buffalo is a large center with a tremendous number of patients that get dental care every year, recruiting will be solely from the patients of the school through flyers near every entrance, exit, stairs, and elevator.

6.0 Inclusion and Exclusion Criteria

6.1 Describe the criteria that define who will be **included** in your final study sample.

NOTE: This may be done in bullet point fashion.

Response:

- 1- The patients should be above 18 years old.
- 2- The presence of Miller's class I or II gingival recession on at least two matching bilateral or contralateral gingival recession defects (≥ 2 mm).
- 3- Recession defect on maxillary incisors, maxillary and mandibular canines, or premolars.
- 4- Absence of a history of periodontal surgery at the involved sites in the last 12 months.

- 5- History of compliance with oral hygiene instructions and periodontal recall.
- 6- Sufficient palatal or tuberosity donor tissue thickness (> 2mm).

6.2 Describe the criteria that define who will be **excluded** from your final study sample.

NOTE: This may be done in bullet point fashion.

Response:

- 1- Patients with systemic illness known to affect the outcome of periodontal therapy, including diabetes, immune deficiencies, etc.
- 2- Pregnant and lactating women
- 3- History of allergic reactions to drugs or materials used in the surgery including collagen.
- 4- Current use of any form of tobacco.

6.3 Indicate specifically whether you will include any of the following special populations in your study using the checkboxes below.

NOTE: Members of special populations may not be targeted for enrollment in your study unless you indicate this in your inclusion criteria.

Response: none

- Adults unable to consent
- Individuals who are not yet adults (infants, children, teenagers)
- Pregnant women
- Prisoners

6.4 Indicate whether you will include non-English speaking individuals in your study. **Provide justification if you will exclude non-English speaking individuals.**

*In order to meet one of the primary ethical principles of equitable selection of subjects, non-English speaking individuals may **not** be routinely excluded from research as a matter of convenience.*

In cases where the research is of therapeutic intent or is designed to investigate areas that would necessarily require certain populations who may not speak English, the researcher is required to make efforts to recruit and include non-English speaking individuals. However, there are studies in which it would be reasonable to limit subjects to those who speak English. Some examples include pilot studies, small unfunded studies with validated instruments not available in other languages, studies with

numerous questionnaires, and some non-therapeutic studies which offer no direct benefit.

Response:

English speaking individuals only, Due to the small size of the study, we do not expect to encounter non-English speakers. There are also a large number of questionnaires involved in this study. Therefore it is reasonable to limit subjects to those who speak English.

7.0 Vulnerable Populations

If the research involves special populations that are considered vulnerable, describe the safeguards included to protect their rights and welfare.

NOTE: You should refer to the appropriate checklists, referenced below, to ensure you have provided adequate detail regarding safeguards and protections. You do not, however, need to provide these checklists to the IRB.

7.1 For research that involves **pregnant women**, safeguards include:
NOTE CHECKLIST: Pregnant Women (HRP-412)

Response:

N/A: This research does not involve pregnant women.

7.2 For research that involves **neonates of uncertain viability or non-viable neonates**, safeguards include:
NOTE CHECKLISTS: Non-Viable Neonates (HRP-413), or Neonates of Uncertain Viability (HRP-414)

Response:

N/A: This research does not involve non-viable neonates or neonates of uncertain viability.

7.3 For research that involves **prisoners**, safeguards include:
NOTE CHECKLIST: Prisoners (HRP-415)

Response:

N/A: This research does not involve prisoners.

7.4 For research that involves **persons who have not attained the legal age for consent to treatments or procedures involved in the research (“children”)**, safeguards include:
NOTE CHECKLIST: Children (HRP-416)

Response:

N/A: This research does not involve persons who have not attained the legal age for consent to treatments or procedures (“children”).

7.5 For research that involves **cognitively impaired adults**, safeguards include:
NOTE CHECKLIST: Cognitively Impaired Adults (HRP-417)

Response:

N/A: This research does not involve cognitively impaired adults.

7.6 Consider if other specifically targeted populations such as students, employees of a specific firm, or educationally or economically disadvantaged persons are vulnerable. **Provide information regarding their safeguards and protections, including safeguards to eliminate coercion or undue influence.**

Response:

No specifically targeted populations will be included.

8.0 Eligibility Screening

8.1 Describe **screening procedures** for determining subjects' eligibility. Screening refers to determining if prospective participants meet inclusion and exclusion criteria.

Include all relevant screening documents with your submission (e.g. screening protocol, script, questionnaire).

Response: Subjects who contacted the clinics over the phone will be assessed for their willingness to participate in the study and upon their approval they will be scheduled for a screening visit and will be evaluated according to the inclusion and exclusion criteria. Also, comprehensive patient evaluation including eligibility questionnaire, complete medical and dental history, full mouth examination, periodontal charting, and full-mouth radiographic x-rays and photos will be taken for affected and non-affected sites. Urine pregnancy test will be performed when needed to assure eligibility of interested women.

N/A: There is no screening as part of this protocol.

9.0 Recruitment Methods

N/A: This is a records review only, and subjects will not be recruited. NOTE: If you select this option, please make sure that all records review procedures and inclusion/exclusion screening are adequately described in other sections.

9.1 Describe when, where, and how potential subjects will be recruited.

NOTE: Recruitment refers to how you are identifying potential participants and introducing them to the study. Include specific methods you will use (e.g. searching charts for specific ICD code numbers, Research Participant Groups, posted advertisements, etc.).

Response:

Posted advertisements that contain the clinics contact name and number will be distributed throughout the three floors of the School of Dental Medicine- SUNY at Buffalo near the entrances, exits, stairs, and elevators. And throughout the SUNY at

Buffalo campus. Also, advertisement will be posted on PST Doctor's forum, PST social media (facebook and instagram) directed towards potential participant and doctors, Dental Town, American Academy of Periodontology Forum, Dentistry Today Magazine, Compendium Dental Journal, Email list of PST certified doctors in the NY state area, DentMat emailing list to doctors in the NY state area, Geistlich emailing list to doctors in a 100 miles radius around Buffalo including Ontario, Canada, and any posted media including craigslist. Also the study will be advertised through radio and TV interviews with the PI and/or study members. We will also utilize the services of The CTSI Community Engagement Team (CET) to assist in subject recruitment. The CET hosts the Buffalo Research Registry (BRR) that can connect us to community members who have completed a health profile and have agreed to be contacted about potential research opportunities that they may be an interested in based on their self-reported information. The CET also goes out and tables at many events in the community throughout the year and they have agreed to have the IRB approved flyer for this project at the table. They attend events such as Good for the Neighborhood hosted by Independent Health Foundation, UB on the Green, Juneteenth, Elmwood Arts Festival and many others. The CET also hosts a standing table at Conventus on the 4th floor of UBMD where the IRB approved flyer can be spotlighted as well. Newspaper ad will be posted directed towards participants.

Upon calling the clinics, the subjects will be asked some questions over the phone about their willingness to participate in the study and if they agree, they will be scheduled for screening visit.

9.2 Describe how you will protect the privacy interests of prospective subjects during the recruitment process.

NOTE: Privacy refers to an individual's right to control access to him or herself.

Response:

Patients will be informed about the study in the dental clinic in private. The subject controls their own privacy interests, as they will contact the study team if they are willing to participate in the research.

9.3 Identify any materials that will be used to recruit subjects.

NOTE: Examples include scripts for telephone calls, in person announcements / presentations, email invitations.

 *For advertisements, include the final copy of printed advertisements with your submission. When advertisements are taped for broadcast, attach the final audio/video tape. NOTE: You may submit the wording of the advertisement prior to taping to ensure there will be no IRB-required revisions, provided the IRB also reviews and approves the final version.*

Response:

Posted advertisement will be posted that include some information about the study.

10.0 Procedures Involved

10.1 Provide a description of **all research procedures or activities** being performed and when they are performed once a subject is screened and determined to be eligible. Provide as much detail as possible.

NOTE: This should serve as a blueprint for your study and include enough detail so that another investigator could pick up your protocol and replicate the research. For studies that have multiple or complex visits or procedures, consider the addition of a schedule of events table in in your response.

Response:

Pre-surgical treatment:

Upon recruitment of eligible candidates, at-least two matching bilateral or contralateral gingival recession defects are assigned as one tooth will receive the test (PST) technique and one tooth will receive the control (CTG) technique. The first tooth will be randomly assigned to one of the two techniques by opening a prepared randomization schedule letter for each patient that would include which quadrant will be treated first with the Pinhole technique. This will assure that there is equal distribution of whether the PST technique or the CTG technique is performed first. The patients will be blinded of which technique is applied to each of their teeth, and the independent clinical examiner, who will only perform the pre-operative and the 6 weeks, 3, 6, 12, 18, and 24 months evaluations and measurements visits, will be blinded on which technique was used.

The initial therapy will consist of oral hygiene instructions, correction of the recession etiological factor(s), and dental prophylaxis as needed. Two weeks evaluation of adequate oral hygiene and control of gingival inflammation (PI and GI<15%)²⁷ is carried out, and if adequate the first surgical procedure will be performed the same visit after reviewing the surgical consent with the subjects. While, the second surgical procedure for the other sites receiving the comparative technique will be performed 3 weeks later by the same surgeon.

Surgical treatment:

All teeth with recession defects will be treated upon patient's needs, and only two matching bilateral or contralateral gingival recession defects will be included in the statistical analysis. All surgeries are performed by the same expert periodontist.

At the beginning of each surgery a timer will be started to compare operator's time for each technique, and another timer will be used at the suturing stage of the CTG Technique. Both surgical techniques will require achieving local anesthesia using 2% Lidocaine with 1:100,000 epinephrine, all recession defects are thoroughly scaled using curettes (Gracey Curettes, Hu-Friedy, Chicago, IL, USA) and any root surface deposit, soft cementum, root prominence, or irregularities are eliminated to allow for proper graft adaptation and adequate blood supply. For the sites receiving the control technique (Connective Tissue Graft), the technique

described by Langer B. and Langer L. will be performed starting with a sulcular incision followed by a partial thickness flap with two vertical incisions to the mucogingival junction placed at least one-half to one tooth wider mesiodistally than the area of gingival recession. The interproximal papillae are left intact⁵. A CTG is then harvested according to the technique described by Bruno,²⁹ the first incision is perpendicular to the 2nd premolar and 1st molar and is 2-3 mm apical to their gingival margin and as wide as the recipient site, followed by a second incision parallel to the for mentioned teeth and is 1-2 mm apical to the first incision, then the CTG is raised by periosteal elevator and released from apical and lateral attachments by sharp incision when needed. The graft is then prepared to have a homogenous thickness of 1.5-2 mm. The donor CTG is stabilized to the underlying connective tissue interproximally using 4-0 Vicryl sutures. The recipient flap is re-positioned coronally, to cover as much as possible of the graft with no tension, 2 mm coronal to the CEJ, then sutured with 4-0 Vicryl sutures. For the sites receiving the test technique ([name] Pinhole Surgical Technique)²⁰ the surgery starts with a small pinhole opening in the alveolar mucosa apical to the mucogingival junction of the affected tooth, the flap is then undermined using special instruments to create a full thickness pouch, followed by extending the pouch horizontally and coronally to undermined the adjacent papilla without incising it and free the flap for its coronal displacement. Then multiple 2x12mm strips of collagen resorbable membrane material (Bio-Gide, Geistlich Pharma AG) are packed under the papilla to secure the flap in a coronal direction. Gentle pressure is applied for 5 minutes to minimize the thickness of the blood clot after each of the procedures. The patients are advised to brush all teeth and sites except the buccal surfaces of the operated-on teeth, which are to be cleaned with 0.12% Chlorhexidine mouth rinse. Patients will be seen at day 1 and 2 weeks for follow-up, healing and pain index will be recorded and a checklist will be used to assess the patient's post-operative condition, also at 2 weeks follow-up prophylaxis will be performed away from gingival margins of operated on teeth. Sutures to be removed two weeks after the surgery for the CTG sites. Six weeks after the surgery, the patients can resume mechanical tooth cleaning in the operated areas using a post-operative ultra soft-bristle brush and will receive prophylaxis teeth cleaning at the clinics. Patients will be asked to record the name of the pain medications taken, frequency, and dosage while also recording the pain index on daily basis for the first 3 weeks after the surgery. All measurements will be recorded at 6 weeks, 3, 6, 12, 18, and 24 months post-operatively for each procedure and oral hygiene reinforced. Six and 12 months prophylaxis will be performed.

The following measurements will be recorded at baseline, 6 weeks, 3, 6, 12, 18, and 24 months post-surgically:

- I. Complete root coverage (CRC): The number of sites that resulted in 100% root coverage.
- II. Recession Depth (RD): Measured in millimeters from the gingival margin at the mid-buccal aspect of the root, to the CEJ or relative CEJ.

- III. Percentage root coverage (%RC): calculated as $([RD \text{ preoperative} - RD \text{ postoperative}] / RD \text{ preoperative}) \times 100\%$.
- IV. Recession classification: The recession type will be classified according to the criteria suggested by Miller
- V. Probing depth (PD): Measured in millimeters from the gingival margin to the base of the periodontal sulcus at 6 sites per tooth.
- VI. Clinical attachment level (CAL): Measured in millimeters from CEJ or relative CEJ to the base of the periodontal sulcus at 6 sites per tooth.
- VII. Width of the keratinized tissue (KTW): Measured in millimeters at mid-buccal aspect of the tooth from the gingival margin to the mucogingival junction.
- VIII. Gingival Thickness: Measured in millimeters at the mid-buccal of the gingiva and 2 mm apical the gingival margin at the attached gingiva or the alveolar mucosa using a #15 endodontic reamer with a silicon disk stop.
- IX. Plaque index (PI): Is used for estimating the status of oral hygiene by measuring dental plaque that occurs in the areas adjacent to the gingival margin.
- X. Gingival index (GI): GI is measured according to Loe and Sillness and scored on a scale of 0 to 3.

More measurements include:

- ❖ Healing index (HI): A horizontal scale from 1-5 evaluating tissue color, response to palpation, granulation tissue, incision margin, suppuration, adopted from Aleksic²⁵. To be assessed at day 1 and 2 weeks post-surgically as follows:
 - 1 (very poor)= $\geq 50\%$ of the gingiva is red, bleeding on palpation, presence of granulation tissues, incision margin not epithelialized (loss of epithelium beyond incision margin), and presence of suppuration.
 - 2 (poor)= $\geq 50\%$ of the gingiva is red, bleeding on palpation, presence of granulation tissues, incision line not epithelialized (connective tissue exposed), and no suppuration.
 - 3 (good)= 25-50% of the gingiva is red, no bleeding on palpation, no granulation tissues, no connective tissue exposed, and no suppuration.
 - 4 (very good)= $< 25\%$ of the gingiva is red, no bleeding on palpation, no granulation tissues, no connective tissue exposed, and no suppuration.

- 5 (excellent)= all tissues are pink, no bleeding on palpation, no granulation tissues, no connective tissue exposed, and no suppuration.
- ❖ Pain index (PN): Pain is recorded on a horizontal pain scale of 0-10, Pain index to be recorded by the patients at 9 am, 3pm, and 9 pm from the day of the surgery and for 3 weeks post-treatment. Also, the patients will be asked to record the name of pain medications taken, dosage, and frequency for the 3 weeks after the surgery. Pain index as follows; Mild for “0 to 3,” moderate for “4 to 6,” and severe for “7 to 10.” None to minimal pain meant little or no discomfort; moderate was any pain that bothers the patient and mildly affects normal daily functions and activities; and severe is considered any pain that could not be tolerated and even disrupts the patient’s daily functions or activities ²⁶.
- ❖ Patient’s Condition Checklist: the patient’s condition will be assessed Patient’s Condition Checklist: the patient’s condition will be assessed according to a pre-set checklist at day 1 and 2 weeks post-surgically, as follows:
 - Clinical appearance of the face: Swelling: severity (mild, moderate, severe), location, lymph nodes, hard or fluctuant, hot or normal temperature; coloration.
 - Bleeding: if yes, location, nature (persistent, intermittent, stops with pressure).
 - Infection or sloughing: if yes, location, extent in mm vertically and horizontally, probable cause of infection.
 - Patient temperature.
 - Pain medications taken: name, dosage, quantity.
 - Photos will be taken.
- ❖ Time: surgical time will be calculated for each surgical procedure from the time of surgical incision or pinhole creation to the conclusion of the surgery; also the time of suturing will be calculated for CTG.

10.2 Describe what data will be collected.

NOTE: For studies with multiple data collection points or long-term follow up, consider the addition of a schedule or table in your response.

Response: recession depth, recession classification, percentage root coverage, percentage complete root coverage, probing depth, clinical attachment level, width of keratinized tissue, gingival thickness, plaque index, and gingival index at baseline, 6 weeks, 3, 6, 12, 18, and 24 months post-surgically. Also, pain index and the name of post-operative pain medication taken, dosage, and frequency will be recorded for the 3 weeks following the surgery and healing index at 1 day and 2 weeks following the surgery with patient's condition checklist. Additionally, Surgical time for each surgical procedure and suturing time for CTG will be calculated at the surgical visit.

10.3 List any instruments or measurement tools used to collect data (e.g. questionnaire, interview guide, validated instrument, data collection form).

Include copies of these documents with your submission.

Response: Standardized periodontal probe 12 UNC (Hu-Friedy, Chicago, IL) for periodontal measurements

Telephone screening script, periodontal charting form, medical and dental history form, eligibility questionnaire, patient's condition checklist, data collection forms, pain index, and healing index.

10.4 Describe any source records that will be used to collect data about subjects (e.g. school records, electronic medical records).

Response:

Patient's chart for full dental and medical history, radiographic x-rays to identify the extent of disease.

10.5 Indicate whether or not **individual** subject results, such as results of investigational diagnostic tests, genetic tests, or incidental findings will be shared with subjects or others (e.g., the subject's primary care physician) and if so, describe how these will be shared.

Response:

Any finding that might lead us to suspect an underlying medical condition, the patient will be notified and advised to follow with primary care physician at the same time. Recommendation for treatment of other teeth or sites will be made when needed as a full mouth periodontal exam will be performed for all initially illegible patients, the findings and the results of the study will be included in a report and will be shared with the patients at the end of the study.

10.6 Indicate whether or not **study** results will be shared with subjects or others, and if so, describe how these will be shared.

Response:

The study results are to be published in a respected specialized journal. Also, the study results will be shared with the subjects and any future treatment recommendations will be given to all subjects if needed.

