17.0 Data Management and Analysis

17.1 *Describe the data analysis plan, including any statistical procedures. This section applies to both quantitative and qualitative analysis.*

Response: The main aim of this study is to assess the efficacy of the pinhole surgical technique in treating gingival recession compared to an established surgical treatment method. We therefore will focus in this clinical trial on one primary endpoint, namely recession depth. The change in recession depth during the study observation period will therefore be used for the calculation of sample size.

We previously have calculated the sample size based on parameter estimates gathered from published studies. We now have recalculated the sample size and used parameters estimates generated from 28 cases already treated in this clinical trial. This should give more accurate parameters to calculate the sample size needed. We also used the 80% power. Accordingly, we used the following assumptions to calculate the sample size:

Standard deviation in the group A: 0.91

Standard deviation in the group B: 0.95

Correlation: 0.46

Effect size (the difference in the reduction in recession depth between the test and control groups): 0.4 mm

Level of significance: 0.05

Power: 80%

Type of test: 2-sided

Based on these assumptions, the sample size is 48. In addition, we anticipate a drop out of 4 subjects. Hence, the total number of participants needed for this study is 52.

17.2 *If applicable, provide a power analysis.*

NOTE: This may not apply to certain types of studies, including chart/records reviews, survey studies, or observational studies. This question is asked to elicit whether the investigator has an adequate sample size to achieve the study objectives and justify a conclusion.

Response: Please see item 17.1

17.3 *Describe any procedures that will be used for quality control of collected data.*

Response:

Standardization of measurement and radiographs and assurance of intraoperator reproducibility will be performed.

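### The protocol describes inconsistently what the randomisation letter fixes; read literally, the letter puts PST first in every patient and cannot give the claimed balance of surgical order

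*Protocol*

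**What the plan says.** The design is a "Randomized, split-mouth, double blinded design clinical trial" (protocol, section 4.1). Each patient contributes two matching defects, one treated with each technique.

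The pre-surgical part of section 10.1 makes four statements that bear on allocation and order:

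- The random element is stated as: "The first tooth will be randomly assigned to one of the two techniques".
- The means of doing this is given as "opening a prepared randomization schedule letter for each patient that would include which quadrant will be treated first with the Pinhole technique".
- The result claimed for the procedure is: "This will assure that there is equal distribution of whether the PST technique or the CTG technique is performed first".
- Later in the same part, on the interval between operations: "the second surgical procedure for the other sites receiving the comparative technique will be performed 3 weeks later by the same surgeon".

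No other section says which site is operated on first or adds to the description of the letter.

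**The concern.** A split-mouth trial with staged surgery has two things to allocate: which site receives which technique, and which technique is done first. The protocol claims balance on the second, but the content it gives for the letter does not clearly determine it.

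Order could matter on the protocol's own schedule. The second operation comes three weeks after the first, while mechanical cleaning of the first site resumes only at six weeks (section 10.1). The check of oral hygiene and inflammation is described only before the first operation. The three-week pain and analgesic diary for the first operation ends about when the second begins. Section 2.1 lists pain and healing among the primary endpoints, and section 10.1 compares operating time between techniques. A patient's first and second operations are therefore not obviously interchangeable.

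If one technique were always first, no analysis of those patients could separate technique from order.

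**Working it through.** **Step 1: the statements side by side.**

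| Reading of the letter | What is randomised | Does equal order follow? |
|---|---|---|
| It names the quadrant operated on first, and that operation is PST (literal) | Side only | No. PST is first in every patient |
| It names the quadrant that receives PST | Side-to-technique | Not from the letter. No rule says which quadrant is operated on first |
| It assigns a technique to the first tooth (opening of the sentence) | Order | Yes, if the list is balanced. The text does not say how the first tooth is identified |

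The first reading contradicts the claim of equal order. The second leaves it unsupported. The third is compatible with it, but does not match the content given for the letter.

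**Step 2: the plan's own figure.** Inputs from section 17.1: SDs 0.91 and 0.95, correlation 0.46, difference 0.4 mm, two-sided 0.05, power 80%.

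- SD of the paired difference = √(0.91² + 0.95² − 2 × 0.46 × 0.91 × 0.95) = √(0.8281 + 0.9025 − 0.7953) = √0.9353 = 0.967.
- Normal approximation: n = (0.967 × (1.960 + 0.842) / 0.4)² = 45.9, so 46.
- Paired t-test with the noncentral t distribution: power is 0.793 at n = 47 and 0.801 at n = 48. So n = 48, and 48 + 4 dropouts = 52.

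The stated 48 and 52 reproduce. Neither depends on order.

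**Step 3: how an order effect would enter.** Let τ be the true PST minus CTG difference in recession reduction, π the first-minus-second operation effect, and p the proportion of patients with PST first. A pair with PST first has expected difference τ + π, and a pair with CTG first has τ − π. The mean is

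τ + (2p − 1)π.

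With p = 1/2 the order effect cancels. With p = 1 it enters in full.

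**Step 4: illustration for p = 1, τ = 0, 48 pairs, SD 0.967.** The protocol gives no value for π, so the range is assumed. The noncentrality is π√48 / 0.967.

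| Assumed π (mm) | Probability of two-sided rejection |
|---|---|
| 0.1 | 0.108 |
| 0.2 | 0.289 |
| 0.3 | 0.558 |
| 0.4 | 0.801 |

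The last row equals the design power, because an order effect of 0.4 mm cannot be told apart from the design difference of 0.4 mm.

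**Step 5: balance has to be built into the list.** If order were assigned by simple randomisation, which the protocol does not say, 52 patients would split exactly 26:26 with probability C(52, 26) / 2⁵² = 0.110.

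**The case against.** The strongest reply is that the clause about the letter is only loosely worded and that its context makes the intent plain. The same sentence begins by randomising the first tooth to either technique, and the next says that either may come first in equal numbers. The second operation is called the comparative technique and is not named as CTG. The letter is also said to include the quadrant, which does not mean that it contains nothing else. This stands. A reader might infer that PST is in fact first in everyone and that technique and order are already aliased. The protocol does not support that as a statement of fact.

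A reader might also infer that the operator can steer the easier defect to one technique. Nothing in the protocol says that the operator chooses the first tooth. Choosing it before the letter is opened would favour neither technique on average.

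The figures are conditional too. No source supports an order effect of 0.1 to 0.4 mm on recession reduction, and the mechanisms in the schedule bear more directly on pain, healing and operating time. Follow-up is timed from each procedure, so the three-week gap does not shift the measurement windows. A prepared list may well be balanced, and how it is generated can properly be set out elsewhere, so the 11% chance of an exact split is not a finding against the protocol.

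What the reply does not remove is the conflict itself. The content of the allocation letter is a trial procedure, and the one description of it, followed as written, defeats the property claimed for it in the next sentence.

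**Conclusion.** The concern holds as an internal inconsistency with a possible serious consequence. Section 10.1 claims equal order, but the letter it describes would, on the literal reading, randomise side only and put PST first throughout. On that reading any order effect would pass in full into the technique comparison. For assumed effects of 0.1 to 0.4 mm, with 48 pairs and an SD of the difference of 0.967, false rejection would run from about 11% to 80%. With exactly balanced order there would be no such bias. Which case applies cannot be told from the protocol, and the sample size is unaffected either way. This should be fixed. It is not a demonstrated design failure.

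**What to change.** Replace the allocation sentences in section 10.1 with text such as: *Before the letter is opened, the two study teeth are recorded as site A and site B by position. The letter gives the technique for site A and which technique is performed first, from a list balanced over the four combinations.* Include surgical period in the paired analysis.

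Section 17.1 reports 28 cases already treated. Tabulate the order actually used in them and report results by order. If PST was first in all of them, state that technique and order cannot be separated in those cases.

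If the 28 cases are 28 of the 52 subjects, 24 remain, which allows six per combination. Balancing only these would not fully repair a one-sided start. With 28 + 12 = 40 of 52 having PST first, 2 × 40/52 − 1 = 0.54 of any order effect would stay in the unadjusted difference. This is why the period term is needed.

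The cost is reprinted letters for the remaining subjects, one extra model term and a table of order from existing records.
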